1.2 Rationale

Given the importance of lowering LDL-C and the clinical study data indicating the potential for ezetimibe to enhance the cholesterol lowering properties of statins, this study seeks to characterise the LDL-C lowering potential of an effective statin, rosuvastatin, over a range of doses and to profile the LDL-C lowering properties of these combinations relative to that of the simvastatin/ezetimibe fixed dose combination, including the highest dose of this combination.

With regard to cholesterol absorption, it was recently described that patients having a combination of high LDL-C and high sitosterol levels in plasma also had the highest risk for developing cardiovascular disease. In addition, it has been proposed that cholesterol absorption inhibitors might be most effective in patients being hyperabsorbers (high β -sitosterol levels). Thus, biomarkers for cholesterol absorption (β -sitosterol), cholesterol synthesis (lanosterol) and bile acid synthesis (7-beta-hydroxy-4-cholestene-3-one, C4) will also be analysed.

This study will be conducted in compliance with the protocol and with the International Conference on Harmonisation (ICH) Good Clinical Practice (GCP).

2. STUDY OBJECTIVES

2.1 **Primary objectives**

The primary objective of this study is to evaluate the LDL-C lowering efficacy of rosuvastatin (CRESTORTM) 10 mg and 20 mg in combination with ezetimibe relative to that of simvastatin in a fixed dose combination with ezetimibe. This objective has 3 specific components:

- 1. Percentage change from baseline in LDL-C for rosuvastatin 20mg in combination with ezetimibe 10mg vs simvastatin 40mg in combination with ezetimibe 10mg after 6 weeks combination therapy (mean value of 4 and 6 weeks of combination therapy will be used)
- 2. Percentage change from baseline in LDL-C for rosuvastatin 10mg in combination with ezetimibe 10mg vs simvastatin 40mg in combination with ezetimibe 10mg after 6 weeks combination therapy (mean value of 4 and 6 weeks of combination therapy will be used)
- 3. Percentage change from baseline in LDL-C for rosuvastatin 20mg in combination with ezetimibe 10mg vs simvastatin 80mg in combination with ezetimibe 10mg after 6 weeks combination therapy (mean value of 4 and 6 weeks of combination therapy will be used)

To address the apparent multiple comparisons of rosuvastatin/ezetimibe combinations to simvastatin/ezetimibe fixed dose combinations, the primary objective is constructed of 3 components. There will be a 'family of tests' approach using the Hochberg procedure to adjust for the multiple comparisons and this is detailed in Section 6.

2.2 Secondary objectives

If statistical significance is reached for any of the components of the primary objective, the following secondary objectives (1 to 6) will be formally tested (secondary objectives 7 and 8 and the exploratory objective will be tested even if statistical significance is not reached):

- 1. To assess and compare the effects of rosuvastatin 10 mg in combination with ezetimibe 10 mg vs simvastatin 80 mg in combination with ezetimibe 10 mg on percentage LDL-C reduction after 6 weeks combination therapy (mean value of 4 and 6 weeks of combination therapy will be used)
- 2. To assess and compare the effects of rosuvastatin 10 mg and 20 mg in combination with ezetimibe 10 mg vs simvastatin 40 mg and 80 mg in combination with ezetimibe 10 mg on percentage change in HDL-C, TC, TG, nonHDL-C, ApoB, apolipoprotein A-I (ApoA-I); TC/HDL-C, LDL-C/HDL-C, nonHDL-C/HDL-C, ApoB/ApoA-I and high sensitivity C-reactive protein (hs-CRP) from baseline after 6 weeks of combination therapy (mean value of 4 and 6 weeks of combination therapy will be used)

- 3. To assess the efficacy of rosuvastatin 20 mg in combination with ezetimibe 10 mg vs simvastatin 40 mg in combination with ezetimibe 10 mg on the proportion of patients achieving lipid goals (American and European guideline) after 6 weeks combination therapy (mean value of 4 and 6 weeks of combination therapy will be used)
- 4. To assess the efficacy of rosuvastatin 10 mg in combination with ezetimibe 10 mg vs simvastatin 40 mg in combination with ezetimibe 10 mg on the proportion of patients achieving lipid goals (American and European guideline) after 6 weeks combination therapy (mean value of 4 and 6 weeks of combination therapy will be used)
- 5. To assess the efficacy of rosuvastatin 20 mg in combination with ezetimibe 10 mg vs simvastatin 80 mg in combination with ezetimibe 10 mg on the proportion of patients achieving lipid goals (American and European guideline) after 6 weeks combination therapy (mean value of 4 and 6 weeks of combination therapy will be used)
- 6. To assess the efficacy of rosuvastatin 10 mg in combination with ezetimibe 10 mg vs simvastatin 80 mg in combination with ezetimibe 10 mg on the proportion of patients achieving lipid goals (American and European guideline) after 6 weeks combination therapy (mean value of 4 and 6 weeks of combination therapy will be used)
- 7. To assess the effects of rosuvastatin 10 mg and 20 mg in combination with ezetimibe 10 mg vs the same dose of rosuvastatin 10 mg and 20 mg alone on percentage change in LDL-C, HDL-C, TC, TG, nonHDL-C, ApoB, ApoA-I; TC/HDL-C, LDL-C/HDL-C, nonHDL-C/HDL-C, ApoB/ApoA-I and hs-CRP from baseline and on current American and European guideline lipid goal achievement after 6 weeks monotherapy and 6 weeks of combination therapy (mean value of 4 and 6 weeks of combination therapy will be used)
- 8. To assess the safety and tolerability of rosuvastatin in combination with ezetimibe vs simvastatin in combination with ezetimibe by observing adverse events, changes in laboratory safety variables and discontinuations over 6 weeks of combination therapy

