6. STATISTICAL METHODS AND DETERMINATION OF SAMPLE SIZE

6.1 Statistical evaluation – general aspects

A comprehensive statistical analysis plan (SAP) will be prepared before unblinding of the data, and before database lock.

Experience in previous studies indicates that within-patient fluctuations in LDL-C exhibit autocorrelations lasting a period of several weeks. Thus, overall precision will be increased by using an average of 2 measurements taken at least 2 weeks apart. Since the onset of lipid-lowering treatments is largely complete by 4 weeks, an average of measurements made at 4 and 6 weeks will provide an accurate estimate of the treatment effect throughout this period. In this study, all baseline and on-treatment effects are assessed as the mean of 2

consecutive measurements made 2 weeks apart. For reporting purposes, the average of weeks 4 and 6 is termed the effect after 6 weeks of treatment.

Two-sided tests of statistical significance will be used throughout.

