6.2 Description of outcome variables in relation to objectives and hypotheses

Primary outcome variable:

- Percentage LDL-C change from baseline to 6 weeks (mean of weeks 4 and 6) of combination therapy
- Statistical significance of the following 3 comparisons will be tested simultaneously by a Hochberg procedure to control for multiple comparisons:
 - 1. Rosuvastatin 20 mg + ezetimibe 10mg vs simvastatin 40 mg+ 10 mg ezetimibe
 - 2. Rosuvastatin 10 mg + ezetimibe 10mg vs simvastatin 40 mg+ 10 mg ezetimibe
 - 3. Rosuvastatin 20 mg + ezetimibe 10mg vs simvastatin 80 mg+ 10 mg ezetimibe

Secondary outcome variables:

The secondary outcome variables include:

- LDL-C, HDL-C, TC, TG, nonHDL-C, ApoB, ApoA-I, TC/HDL-C, LDL-C/HDL-C, nonHDL-C/HDL-C and ApoB/ApoA-I, hs-CRP; and the corresponding measures of effects are the respective changes from baseline
- Therapeutic lipid goals as described in American and European guidelines, with the corresponding measures of effect being the proportions of patients achieving goal

Exploratory

• Change in biomarkers (sitosterol, lanosterol, C4 and LpPLA2). An additional sample will also be drawn for possible other biomarkers and lipid fractions that are related to atherosclerosis

Clinical Study Protocol Drug Substance Rosuvastatin Study Code D356FC00003 Date

Safety

- AEs
- Vital signs (blood pressure and pulse rate)
- Clinical chemistry
- Haematology
- Urinalysis

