6.4 Method of statistical analysis

The primary analysis will be made on LDL-C as the LOCF in the ITT population. A supportive analysis will be made on the completer ITT population.

Lipids and lipoproteins (as part of the secondary objectives) are: TC, LDL-C, HDL-C, TG, ApoA-I, ApoB, nonHDL-C, ApoB/ApoA-I, TC/HDL-C, LDL-C/HDL-C, nonHDL-C/HDL-C and hs-CRP. Baseline for calculating percentage change in a lipid or lipoprotein will be the mean of values from Visits 2 and 3 (Weeks -2 and 0). Monotherapy will be assessed as the mean of Visits 4 and 5 (Weeks 4 and 6), and combination therapy will be assessed as the mean of Visits 6 and 7 (Weeks 10 and 12).

The effect of combination therapy will be assessed by analysis of co-variance (ANCOVA) using geometric percentage change, where the response variable is the logarithm of the ratio of the treatment value divided by the corresponding baseline value, and treatment and centre are the explanatory variables. Estimates of treatment effect, and their 95% CI, will be exponentiated to produce estimates of percentage change. For comparison with other studies, point estimates and confidence intervals will also be calculated arithmetically on the percentage change from baseline. However, the p-values for specified comparisons will be calculated for the geometric analysis only.

The estimates of the additional effects on lipids and lipoproteins of adding ezetimibe 10 mg to rosuvastatin 10 mg or 20 mg will be calculated in the same way using the geometric mean of the 2 monotherapy visits as baseline. Corresponding 95% CIs will be computed.

Depending on the distribution of patients across centres, it may be sensible to pool some small centres together by region. This will be discussed and agreed by biostatistical personnel and the clinical team at AstraZeneca before database lock.

The numbers and percentages of patients reaching appropriate goals will be summarised. Since the prescribed goals may change over time, the goals used in the evaluation will represent the current regional guidelines for this patient population at the time when the SAP is finalised (prior to database lock).

Formal analysis will be by logistic regression with terms for baseline LDL-C, centre and treatment in the model. Hypothesis testing in logistic regression models will be performed using likelihood ratio tests.

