6.5 Determination of sample size

The size of the study population is based upon the primary endpoint, the percentage reduction in LDL-C after 4 to 6 weeks of combination therapy, and the following treatment comparisons:

- rosuvastatin 10 mg plus ezetimibe 10 mg vs simvastatin 40 mg plus ezetimibe 10 mg
- rosuvastatin 20 mg plus ezetimibe 10 mg vs simvastatin 40 mg plus ezetimibe 10 mg
- rosuvastatin 20 mg plus ezetimibe 10 mg vs simvastatin 80 mg plus ezetimibe 10 mg

These endpoints will be tested sequentially using the Hochberg procedure.

Power is calculated for simultaneously attaining all 3 endpoints. Since the success of the rosuvastatin 20 mg plus ezetimibe 10 mg vs simvastatin 40 mg plus ezetimibe 10 mg is essentially assured when the other 2 comparisons are met, the power calculation is based on those contrasts. In order for the overall power of the study to be 90%, each of the 2 contrasts must have approximately 95% power.

The rosuvastatin/ezetimibe combinations in this study have not been previously studied in large populations and so the effect size of these treatments is not known with certainty. Based

on the relative potencies observed for rosuvastatin and simvastatin monotherapies, and the approximately uniform supplemental effect of ezetimibe used with various statins, it is reasonable to assume an effect size of approximately 5% for the 2 comparisons between the rosuvastatin and simvastatin combinations, with a standard deviation (SD) of mean percentage reduction of 13%. This SD assumes a variance reduction because of the use of averages of replicates. Under these assumptions, a sample size of 177 ITT patients per arm is required.

Further exploratory calculations, based on logarithmic analysis and incorporation of an apparent increase in variation with increasing lipid-lowering effect, supported this conclusion.

It is anticipated that there will be a screen-failure rate of up to approximately 65% during the dietary lead-in phase and a dropout rate of 10% following randomisation.

Using this information, approximately 2285 patients will enter into the dietary lead-in phase, of whom 800 (approximately 200 per arm) will be randomised to receive study treatment.

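### Opening secondary objectives 1-6 to formal testing after any one primary success gives only weak error control, so their results cannot be called confirmatory

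*Protocol*

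**What the plan says.** Section 2.2, repeated in the synopsis, sets the condition for the secondary objectives: "If statistical significance is reached for any of the components of the primary objective, the following secondary objectives (1 to 6") go forward to formal testing. Objectives 7 and 8 and the exploratory objective are exempt from the condition.

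The primary family has its own adjustment. Section 6.2 says: "Statistical significance of the following 3 comparisons will be tested simultaneously by a Hochberg procedure to control for multiple comparisons". Sections 2.1, 3.2.1 and 6.5 agree. For objectives 1-6 the protocol describes no adjustment, order or share of alpha. The remark in Section 3.2.1 that no further adjustment is needed concerns the additivity of ezetimibe and rosuvastatin (objective 7).

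No numeric test level is given. Section 6.1 says "Two-sided tests of statistical significance will be used throughout", and Section 6.4 uses 95% confidence intervals.

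Section 6.5 powers the trial to win all three primary comparisons: "In order for the overall power of the study to be 90%, each of the 2 contrasts must have approximately 95% power".

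**The concern.** The protocol puts a gate in front of objectives 1-6 and leaves 7 and 8 outside it, so the gate is evidently meant to protect the formal secondary tests. It does so only if it stays shut when it should.

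After Hochberg rejects one of three hypotheses, the other two still hold the alpha. None can be handed in full to a second family while any primary hypothesis stands unrejected. A gate that opens on any single success can therefore pass on alpha that is not available.

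At stake are claims on rosuvastatin 10 mg versus simvastatin 80 mg (objective 1), on eleven other lipid, lipoprotein and inflammation variables (objective 2), and on goal attainment (objectives 3-6). A reader could take these as confirmatory when the rule does not support that.

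**Working it through.** **Inputs.** From Section 6.5: difference 5 points on each of the two powered contrasts, SD 13, 177 ITT patients per arm, 95% power per contrast, 10% dropout. From Section 6.1: two-sided tests. Assumed: a 5% level.

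**The plan's own figure.** n per arm = 2 × (1.960 + 1.645)² × 13² / 5² = 175.7, so 176. The t-based version gives 176.7, so 177, as stated. Dropout: 177 / 0.90 = 196.7, consistent with about 200 per arm. The inferred 5% level thus reproduces the protocol's sample size; a level of 2.5% per contrast would need 205.

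**When the gate opens.** Order the three primary p-values from smallest to largest. Hochberg rejects at least one hypothesis if the smallest is ≤ 0.05/3 = 0.0167, or the second is ≤ 0.025, or the largest is ≤ 0.05.

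By hand, suppose only rosuvastatin 20 mg versus simvastatin 40 mg truly differs, by 5 points. The standard error of a difference is 13 × √(2/177) = 1.382, so the expected z is 5 / 1.382 = 3.618. The two-sided critical value at 0.0167 is 2.394. The power at that step is Φ(3.618 − 2.394) = Φ(1.224) = 0.89. The other two Hochberg routes bring it to about 0.90.

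Simulation of the four arm means, with contrasts sharing arms:

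| True situation | Gate opens on any success | All three rejected |
|---|---|---|
| No primary comparison differs | about 5% (4.6-4.7%) | 0.1% |
| Only rosuvastatin 20 vs simvastatin 40 differs, by 5 points | 90% | 0.2% |
| Same, by 8 points | over 99.9% | 0.2-0.3% |
| Both powered contrasts 5 points, simvastatin 80 equal to 40 | 99.2% | 88% |
| Same, simvastatin 80 better than 40 by 3 points | 99.98% | 90% |
| Same, by 6 points | 100% to the precision run | 91% |

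The protocol does not state the simvastatin 80 versus 40 difference, so it is shown as a range.

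**Number of tests behind the gate.** Objective 1: 1. Objective 2: 11 variables × 4 pairwise comparisons = 44. Objectives 3-6: 4 comparisons × 2 guidelines = 8. Total 1 + 44 + 8 = 53. This assumes four pairwise tests per variable and one goal per guideline.

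**Error per variable.** If a variable is truly null and its four pairs are each tested at 5%, the chance of at least one false positive is 16%. The contrasts share arms, so this is below the independent value 1 − 0.95⁴ = 18.5%.

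**Putting the two together.** When only rosuvastatin 20 mg versus simvastatin 40 mg differs by 5 points, one truly null variable, unrelated to LDL-C, has a false claim in about 0.90 × 0.16 = 14% of trials. With an all-three gate the bound is the 0.2% of trials in which that gate opens.

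**The case against.** Much of the case on the other side is sound.

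- A reader might infer that the gate protects nothing. It does protect: if no primary comparison truly differs it opens in about 5% of trials, which holds the secondary false-positive rate near that figure. That is weak control, and the point is its limit.
- A reader might infer that the protocol itself regards one primary comparison as certain. Section 6.5 says that rosuvastatin 20 mg versus simvastatin 40 mg "is essentially assured when the other 2 comparisons are met". The statement is conditional and serves to justify powering on two contrasts. It says nothing about trials where those two fail. The near-certain opening follows from the planning figures.
- A reader might infer that the secondary tests run at a full 5%. No level is stated for them, and the SAP, not shown here, may set a level or an order. What the protocol fixes is the any-success condition, which such an SAP would have to override to obtain strong control.
- Treating all 53 tests as independent and truly null gives 1 − 0.95⁵³ = 93%. That is no realistic estimate: TC, nonHDL-C and the ratios are tied to LDL-C and to one another through the Friedewald equation (Section 4.6.1.1). The count itself could be lower, because Section 6.4 gives hs-CRP an overall Kruskal-Wallis test with pairwise Wilcoxon tests only where needed, and leaves the goals to be fixed when the SAP is finalised.
- Under plan, all three primaries succeed in about 88-91% of trials. Alpha may then legitimately pass on, so any versus all matters in roughly one trial in ten.

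What remains is that the written condition cannot give strong control across the two families. Even when all three primaries succeed, the protocol describes nothing that controls error within objectives 1-6.

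**Conclusion.** The point holds as a matter of moderate weight. The any-success gate gives weak control only. It opens in 99% or more of trials under the protocol's planning figures, and in about 90% when both powered comparisons are null and rosuvastatin 20 mg versus simvastatin 40 mg differs by 5 points. Findings on objectives 1-6 therefore cannot be called confirmatory under this rule.

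The opening rates assume a two-sided 5% level, SD 13 and 177 per arm. The 16% figure needs only the 5% level and four pairwise tests. The count of 53 rests on the pairwise and one-goal-per-guideline readings.

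The primary conclusion is untouched, because Hochberg controls the three primary comparisons whatever happens afterwards. That is why this is not a must-fix.

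**What to change.** In the synopsis and Section 2.2, replace any with all three components of the primary objective as the condition for formal testing. This is the outcome Section 6.5 already powers at about 90%.

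The all-three gate does not control error inside the secondary family, so add one of two things:

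- a short pre-specified list of key secondary tests under a stated multiplicity method, with everything outside the list labelled nominal; or
- a statement that all p-values for objectives 1-6 are nominal.

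The method or order is the sponsor's choice. A fixed sequence need not start with objective 1, and starting there could be costly. At SD 13 and 177 per arm, its power to show rosuvastatin 10 mg superior is about 58% if it is truly 3 points better than simvastatin 80 mg, and 2.5% if the two are equal. A sequence that stops at the first failure would then often end at step one.

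The cost is a wording change, made before database lock, and fewer formal secondary claims. In particular there would be none when a primary comparison misses, which is about 10% of trials under plan.

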2.3 Exploratory objective

The exploratory objective of this study is as follows:

• To assess and compare the effects of rosuvastatin 10 mg and 20 mg in combination with ezetimibe 10 mg vs simvastatin 40 mg and 80 mg in combination with ezetimibe 10 mg on change in biomarkers (sitosterol, lanosterol, C4 and LpPLA2). An additional sample will also be drawn for possible other biomarkers and lipid fractions that are related to atherosclerosis. Biomarker results will be reported separately from the clinical study report (CSR)

3. STUDY PLAN AND PROCEDURES

3.1 Overall study design and flow chart

This is a 12-week open-label, randomised, parallel-group, multicentre, phase IIIb study to compare the efficacy and safety of rosuvastatin 10 mg and 20 mg in combination with ezetimibe 10 mg and simvastatin 40 mg and 80 mg in fixed dose combination with ezetimibe 10 mg in patients with hypercholesterolaemia and CHD or a CHD risk equivalent, atherosclerosis or a 10-year CHD risk of >20%. Patients will undergo 6 weeks of monotherapy followed by 6 weeks of combination therapy.

This study requires approximately 800 randomised patients (200 patients per arm) with approximately 50% of patients from the US, 25% from Latin America and 25% from Europe. An approximate screen failure rate of 65% is anticipated based on previous studies (eg, ECLIPSE (Faergeman et al 2006) at 62%; EXPLORER (Ballantyne et al 2007) at 61%). It is therefore anticipated that it will be necessary to screen approximately 2285 patients in order to achieve the requisite number of randomised patients. Centres may be discontinued from the study if recruitment rates are poor and new centres will be added if necessary to achieve recruitment goals. Recruitment will be competitive and centres will stop enrolment once the projected total number of patients is recruited.

The study requires a population of male and female patients, 18 years of age or older, with hypercholesterolaemia and CHD or a CHD risk equivalent, clinical evidence of atherosclerosis (see Appendix G) or a Framingham 10-year CHD risk score of >20% (Appendix J).

Potentially eligible patients undergo screening procedures (Week –6; Visit 1) which include a fasting lipid analysis, discontinuation of previous dyslipidemia treatments and enter a 6-week dietary lead-in period (in which they will follow the Therapeutic Lifestyle Change (TLC) diet), during which they have another lipid analysis (at Week –2; Visit 2). Those who fulfil all eligibility criteria (Week -6; Visit 1) and have qualifying lipid values at Visit 2 (LDL-C 130 to 220 mg / dL; triglyceride < 400 mg / dl) are randomly allocated (1:1:1:1) to 1 of 4 treatments (at Week 0; Visit 3):

- Rosuvastatin 10 mg for 6 weeks followed by rosuvastatin 10 mg plus ezetimibe 10 mg for an additional 6 weeks
- Rosuvastatin 20 mg for 6 weeks followed by rosuvastatin 20 mg plus ezetimibe 10 mg for and additional 6 weeks
- Simvastatin 40 mg for 6 weeks followed by simvastatin 40 mg plus ezetimibe 10 mg fixed dose combination for an additional 6 weeks

• Simvastatin 80 mg for 6 weeks followed by simvastatin 80 mg plus ezetimibe 10 mg fixed dose combination for an additional 6 weeks

Patients return for clinic visits at Week 4 (Visit 4), Week 6 (Visit 5), Week 10 (Visit 6), and then at Week 12 (Visit 7) for the end-of-study procedures. Accordingly, the patient participation time is 18 weeks (see Figure 1 and Table 1).

All visits are related to Visit 3 (Week 0), the randomisation visit, which is referred to as the reference visit. The visit windows for all other visits will be ± 4 days (see Table 2). It is important that investigators adhere to the study plan as closely as possible. If the date of an individual visit does not conform to the study plan, the timing of subsequent visits should be planned to maintain the visit structure relative to baseline.

Throughout the treatment phase of the study, from randomisation until final visit, the results of all blood lipid and lipoprotein levels will not be revealed to the study centre personnel. The results can then be provided following last patient completed, data base lock and formal unblinding.

During the course of the study, investigators are encouraged to manage of other cardiovascular risk factors such as hypertension and diabetes according to criteria specified in established guidelines and/or good medical practices, including a diet and exercise advice.

Once patients have completed participation in the study, their subsequent clinical management, including dyslipidemia treatment will be left to the discretion/clinical judgement of the Investigator. Investigators are encouraged to defer post-study lipid analyses until after the patient has instituted post-study dyslipidemia treatment.

There is a proposed optional genetics component to the study (please refer to Appendix K for details). In addition, the biomarkers research is not mandatory for participating patients.

6-week dietary lead-in phase (Visits 1 and 2, Weeks -6 to 0)

Patient eligibility will be assessed and written informed consent must be obtained prior to any visit procedures, including for the biomarker and genetic components of the study. Patients entering the dietary lead-in phase will follow the TLC diet (Appendix I) and are required to discontinue any current lipid-lowering therapy at Visit 1 (Week -6) to ensure that no residual effect on lipids will be carried forward in to the randomised treatment period. As part of the screening procedures, fasting blood samples will be taken for lipid analysis at Visits 1 and 2 (Weeks -6 and -2). In addition, evidence of atherosclerosis/CHD risk will be assessed, along with clinical chemistry, haematology and β -HCG. Medical and surgical history/demography will be recorded, as will concomitant medication and a physical examination, including vital signs, weight, height and waist circumference, will be performed. Dietary counselling will also be provided during the whole study.

12-week randomised treatment phase (Visits 3 to 7, Weeks 0 to 12)

Eligible patients will be randomised to the treatment phase to 1 of 4 treatment groups: rosuvastatin10 mg, rosuvastatin 20 mg, simvastatin 40 mg or simvastatin 80 mg. Treatment of 1 oral tablet will be administered once daily (od) for 6 weeks. After 6 weeks of monotherapy, patients will begin combination therapy, continuing on their previous treatment in combination with ezetimibe 10 mg. Patients randomised to rosuvastatin and ezetimibe combination therapy will receive 2 oral tablets od. Patients randomised to simvastatin and ezetimibe fixed dose combination therapy will receive a single oral tablet od. Tablet bottles will be dispensed at Visit 3 (Week 0) and at Visit 5 (Week 6) and compliance will be checked at Visits 4 to 7 (Weeks 4 to 12). Fasting blood samples for lipid and lipoprotein analysis will be taken at each visit during the treatment phase. Clinical chemistry testing will be performed at all visits during the treatment phase, as will urinalysis; haematology will be assessed at Visits 3, 5 and 7 (Weeks 0, 6 and 12). Concomitant medications and AEs will be recorded at each visit. The mean LDL-C values of Weeks 4 and 6 of combination therapy (Visits 6 and 7) will be used for the primary outcome variable. Optional samples for biomarker analysis will be taken at all visits during the treatment phase and a genetic sample will be taken at Visit 3 (Week 0), if applicable.

[figure not shown]

Figure 1 Study flow chart

Table 1Study plan

	Screening Phase		Randomised Phase				
Visit	1	2	3	4	5	6	7
Visit Description	Dietary lead-in		Statin monotherapy		Statin + Ezetimibe		
No. Weeks	-6 w	-2 w	0 w	4 w	6 w	10 w	12 w
Written informed consent	Х						
Written informed consent for genetic sampling	Х						
Written informed consent for biomarker sampling	X						
Medical and surgical history/demography	Х						
Evidence of atherosclerosis/CHD risk	Х						
Physical examination	Х						X
Vital signs/weight/waist circumference	Х						X
Height	Х						
Concomitant medication	Х	Х	Х	X	Х	X	Х
Dietary counselling	Х	Х	Х	X	Х	X	
Clinical chemistry ^a	Х		Х		Х		Х
Abbreviated clinical chemistry ^b		Х		X		X	
Haematology ^c	Х		Х		Х		Х
Fasting lipids ^d	Х	Х	Х	X	Х	X	Х
Urinalysis ^e			Х	X	Х	X	Х
β-HCG ^f	Х	(X)	(X)	(X)	(X)	(X)	(X)
Genetic sampling ^g			Х				
Biomarker sampling ^h			Х	Х	Х	Х	Х
Eligibility criteria	Х	Х	Х				
Randomisation			Х				
Dispense study medication			Х		Х		
Study drug compliance				Х	Х	Х	X
Adverse events (AEs) ⁱ		Х	Х	Х	Х	Х	Х

- ^a The following clinical chemistry tests are to be performed: albumin, total bilirubin, blood urea nitrogen, CK, serum creatinine, alanine aminotransferase (ALT) (serum glutamic pyruvic transaminase (SGPT)), aspartate aminotransferase (AST) (serum glutamic oxaloacetic transaminase (SGOT)), fasting glucose, alkaline phosphatase, calcium, phosphate, potassium, sodium, total protein, gamma-glutamyl transferase.
- ^b The following abbreviated clinical chemistry tests are to be performed: creatine kinase (CK), serum creatinine, ALT, AST and TSH (TSH only at Visit 2; Week -2).
- ^c Haematology is to consist of: platelet count, haemoglobin, haematocrit, red blood cell (RBC) count, RBC indices (mean cell volume (MCV), mean cell haemoglobin (MCH) and mean cell haemoglobin concentration (MCHC)), white blood cell (WBC) count, WBC differential (neutrophils, bands, lymphocytes, monocytes, eosinophils and basophils).
- ^d Lipids include: TC, LDL-C, HDL-C, TG, nonHDL-C, LDL-C/HDL-C, TC/HDL-C, nonHDL-C/HDL-C, ApoB, ApoA-I, ApoB/A-I, along with hs-CRP. Only lipids required at Visits 1 and 2 (Weeks -6 and -2); lipids, lipoproteins and hs-CRP at Visits 3 to 7 (Weeks 0 to 12).
- ^e For Visits 3, 5 and 7 (Weeks 0, 6 and 12), urinalysis sample is to consist of: visual description (colour and appearance), a dipstick test (specific gravity, pH, protein (qualitative), glucose, ketones, bilirubin and blood), microscopy (RBC, WBC, bacteria, casts and crystals). Quantitative assessment of total protein, albumin and creatinine is to be performed if indicated. For Visits 4 and 6 (Weeks 4 and 10), the following abbreviated urinalysis is to be performed: a dipstick test (specific gravity (if suspected/necessary), protein (qualitative) and blood). Qualitative assessment of total protein, albumin and creatinine is to be performed if indicated.
- ^f An assay of serum β -HCG is only to be performed for women of childbearing potential. After Visit 1 (Week -6), an assay of serum β -HCG is only performed if it is suspected that a woman has become pregnant during the study. Assays of serum β -HCG will be performed on blood samples drawn for the clinical chemistry/abbreviated clinical chemistry testing.
- ^g If consent is not obtained at Visit 1 (Week -6), as per study plan, it can be obtained at any subsequent visits. The genetic sampling is planned for the randomisation visit, but can be taken at a subsequent visit.
- ^h Blood samples for biomarkers, ie, sitosterol, lanosterol, C4 and LpPLA2 will be drawn at randomisation and at the following visits. An additional sample will also be drawn at these visits for other biomarkers and lipid fractions that are related to atherosclerosis. The decision to perform the analyses will be taken after completion of the study.
- ⁱ AEs and serious adverse events (SAEs) will be collected from the time when informed consent is obtained to end of study.

Visit	Visit Description	Visit Window		
Visit 1 (Week -6)	Screening/dietary lead-in	6 weeks (±4 days) before Visit 3		
Visit 2 (Week -2)	Screening/dietary lead-in	2 weeks (±4 days) before Visit 3		
Visit 3 (Week 0)	Randomisation/Treatment	Reference Visit (N/A)		
Visit 4 (Week 4)	Treatment	4 weeks (±4 days) after Visit 3		
Visit 5 (Week 6)	Treatment	6 weeks (±4 days) after Visit 3		
Visit 6 (Week 10)	Treatment	10 weeks (±4 days) after Visit 3		
Visit 7 (Week 12)	Study completion	12 weeks (±4 days) after Visit 3		

Table 2Patient visit design with visit windows

Unscheduled visits

Patients may return for evaluation at any time their condition warrants medical attention. Appendices C, D, E and F provide guidance concerning certain laboratory elevations.

